3.1.5.2 Dose modifications

The following dose modifications will be implemented in case of toxicities:

- Grade 2, 3, or 4 thrombocytopenia:
 - Withhold dosing until resolution to Grade 0 or 1;
 - Resume CAM-H2 at 50% with complete or partial resolution;
 - If a reduced dose does not result in Grade 2, 3, or 4 thrombocytopenia, administer CAM-H2 at the full planned dose for next cycle.
 - Permanently discontinue CAM-H2 for Grade 2 or higher thrombocytopenia requiring a treatment delay of 12 weeks or longer; and
 - Permanently discontinue CAM-H2 for recurrent (defined in this study as occurring after >1 dose of CAM-H2 during Cycle 1) Grade 2, 3, or 4 thrombocytopenia.
- Grade 3 or 4 anemia and neutropenia:
 - Withhold dosing until resolution to Grade 0, 1, or 2;
 - Resume CAM-H2 at 50% in patients with complete or partial resolution;
 - If a reduced dose does not result in Grade 3 or 4 anemia or neutropenia, administer CAM-H2 at full planned dose for next cycle.
 - Permanently discontinue CAM-H2 for Grade 3 or higher anemia or neutropenia requiring a treatment delay of 12 weeks or longer; and
 - Permanently discontinue CAM-H2 for recurrent (defined in this study as occurring after >1 dose of CAM-H2 during Cycle 1) Grade 3 or 4 anemia or neutropenia.
- Renal toxicity (defined as an eGFR <40 mL/minute or a 40% decrease in baseline eGFR):
 - Withhold dosing until resolution to at least 80% of baseline eGFR;
 - Resume CAM-H2 at 50% in patients with complete or partial resolution;
 - If a reduced dose does not result in another decrease of eGFR, administer CAM-H2 at the full, planned dose for next cycle.
 - Permanently discontinue CAM-H2 for eGFR decreases requiring a treatment delay of 12 weeks or longer; and
 - Permanently discontinue CAM-H2 for recurrent (defined in this study as occurring after >1 dose of CAM-H2 during Cycle 1) toxicity.

- Hepatic toxicity (Hy's Law cases):
 - Withhold dosing until resolution to ALT and AST values $<2 \times$ baseline and total bilirubin values of $<1.5 \times$ ULN;
 - Resume CAM-H2 at 50% in patients with complete or partial resolution;
 - If a reduced dose does not result in another transaminase or total bilirubin increase, administer CAM-H2 at full planned dose for next cycle.
 - Permanently discontinue CAM-H2 for transaminase or total bilirubin decreases requiring a treatment delay of 12 weeks or longer; and
 - Permanently discontinue CAM-H2 for recurrent (defined in this study as occurring after >1 dose of CAM-H2 during Cycle 1) toxicity.
- Hepatic toxicity (patients with hepatic metastases and AST or ALT $>8 \times$ ULN or AST or ALT $>5 \times$ ULN for ≥ 14 days):
 - Withhold dosing until resolution to ALT and AST values of $<1.2 \times$ baseline and total bilirubin values of $<1.5 \times$ ULN;
 - Resume CAM-H2 at 50% in patients with complete or partial resolution;
 - If a reduced dose does not result in another transaminase or total bilirubin increase, administer CAM-H2 at full planned dose for next cycle.
 - Permanently discontinue CAM-H2 for transaminase or total bilirubin decreases requiring a treatment delay of 12 weeks or longer; and
 - Permanently discontinue for recurrent (defined in this study as occurring after >1 dose of CAM-H2 during Cycle 1) toxicity.
- Grade 3 or 4 non-hematological toxicities as listed in the CTCAE version 5.0:
 - Withhold dosing until resolution to Grade 0, 1, or 2;
 - Resume CAM-H2 at 50% in patients with complete or partial resolution;
 - If a reduced dose does not result in Grade 3 or 4 toxicity, administer CAM-H2 at full planned dose for next cycle.
 - Permanently discontinue CAM-H2 for Grade 3 or higher toxicity requiring a treatment delay of 12 weeks or longer; and
 - Permanently discontinue for recurrent (defined in this study as occurring after >1 dose of CAM-H2 during Cycle 1) Grade 3 or 4 toxicities.

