- If at least 1 DLT is reported, the SRC recommendation will depend on the DLT profile (ie, identical DLTs in different patients), the frequency and severity of DLTs in the same patient, and the recommendation made by the Investigator; and
- If no DLT is reported, the planned dose escalation may proceed with the next cohort or phase, unless the Investigator has any other safety concerns.

All decisions will be documented in writing and communicated to the study team in a timely manner before dosing in the next cohort can start.

Dose Modifications

The following dose modifications will be implemented in case of toxicities:

- Grade 2, 3, or 4 thrombocytopenia:
 - Withhold dosing until resolution to Grade 0 or 1;
 - Resume CAM-H2 at 50% with complete or partial resolution;
 - If a reduced dose does not result in Grade 2, 3, or 4 thrombocytopenia, administer CAM-H2 at the full planned dose for next cycle.
 - Permanently discontinue CAM-H2 for Grade 2 or higher thrombocytopenia requiring a treatment delay of 12 weeks or longer; and
 - Permanently discontinue CAM-H2 for recurrent (defined in this study as occurring after >1 dose of CAM-H2 during Cycle 1) Grade 2, 3, or 4 thrombocytopenia.
- Grade 3 or 4 anemia and neutropenia:
 - Withhold dosing until resolution to Grade 0, 1, or 2;
 - Resume CAM-H2 at 50% in patients with complete or partial resolution;
 - If a reduced dose does not result in Grade 3 or 4 anemia or neutropenia, administer CAM-H2 at full planned dose for next cycle.
 - Permanently discontinue CAM-H2 for Grade 3 or higher anemia or neutropenia requiring a treatment delay of 12 weeks or longer; and
 - Permanently discontinue CAM-H2 for recurrent (defined in this study as occurring after >1 dose of CAM-H2 during Cycle 1) Grade 3 or 4 anemia or neutropenia.
- Renal toxicity (defined as an eGFR <40 mL/minute or a 40% decrease in baseline eGFR):
 - Withhold dosing until resolution to at least 80% of baseline eGFR;
 - Resume CAM-H2 at 50% in patients with complete or partial resolution;
 - If a reduced dose does not result in another decrease of eGFR, administer CAM-H2 at the full, planned dose for next cycle.
 - Permanently discontinue CAM-H2 for eGFR decreases requiring a treatment delay of 12 weeks or longer; and
 - Permanently discontinue CAM-H2 for recurrent (defined in this study as occurring after >1 dose of CAM-H2 during Cycle 1) toxicity.

- Hepatic toxicity (Hy's Law cases):

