6.2.2.8 Visit 10 (Week 8)

The following procedures will be performed at Visit 10 (Week 8):

- Assess AEs;
- Perform physical examination;
- Measure vital signs;
- Perform clinical laboratory tests;

Note: Clinical laboratory tests should be performed prior to any imaging.

- Perform urinalysis for kidney biomarkers and for microscopic evaluation of sediment;

- Assess performance status using the ECOG PS; and
- Perform imaging to evaluate disease status.

Note: Diagnostic CT scan will be performed in all patients. Brain MRI will only be performed in patients with known brain metastases.

6.2.2.9 Visit 11 (Week 11): End of Treatment Visit or Cycle 2 eligibility assessment

This visit will also serve as the screening visit for Cycle 2 of the dose escalation phase. Cycle 2 eligibility will be assessed by evaluating disease state and safety. This visit will serve as the EOT Visit for patients who do not have CB.

The following procedures will be performed at Visit 11 (Week 11):

- Update demographics and medical history, including confirmation of lesion size;
- Record prior and concomitant medications, including information on any thyroid-blocking drugs;
- Deliver thyroid-blocking drugs for next visit (only patients eligible for and continuing to Cycle 2);

Note: Patients will not take the thyroid-blocking drugs at this visit but will be instructed to take them 24 hours prior to their next visit (ie, 24 hours prior to study drug administration).

- Perform urine hCG testing in all female patients of childbearing potential (ie, ovulating, premenopausal, and not surgically sterile);
- Collect blood to evaluate serum for ADAs and to measure exploratory biomarkers (from patients who have consented to the procedure);
- Assess AEs;
- Measure weight;
- Perform physical examination;
- Measure vital signs;
- Perform clinical laboratory tests;

Note: Clinical laboratory tests should be performed prior to any imaging.

- Perform triplicate 12-lead ECGs;
- Perform echocardiogram;

Note: LVEF may alternatively be measured using a multigated acquisition scan.

- Perform urinalysis for kidney biomarkers and for microscopic evaluation of sediment; and
- Perform imaging to evaluate disease status (EOT Visit only).

Note: Diagnostic CT scan will be performed in all patients. Brain MRI will only be performed in patients with known brain metastases.

Note: If the patient is continuing to Cycle 2, imaging to evaluate disease status will not be performed.

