6.2.3.9 Visits 19, 28, and 37 (Week 8)

The following procedures will be performed at Visits 19, 28, and 37 (Week 8):

- Assess AEs;
- Perform physical examination;
- Measure vital signs;
- Perform clinical laboratory tests;

Note: Clinical laboratory tests should be performed prior to any imaging.

- Perform triplicate 12-lead ECGs;
- Perform urinalysis for kidney biomarkers and for microscopic evaluation of sediment;
- Assess performance status using the ECOG PS; and
- Perform imaging to evaluate disease status.

Note: Diagnostic CT scan will be performed in all patients. Brain MRI will only be performed in patients with known brain metastases.

6.2.3.10 Visits 20, 29, and 38 (Week 11): cycle eligibility or End of Treatment Visit

For Cycles 2 and 3, this visit will also serve as eligibility assessment for the next cycle in patients with CB and a cumulative kidney dose <23 Gy (based on the dosimetry results during Cycle 1). This visit will serve as the EOT Visit for patients who do not have CB and/or a cumulative kidney dose <23 Gy. This will serve as the EOT Visit for all patients in Cycle 4.

The following procedures will be performed at Visits 20, 29, and 38 (Week 11):

- Update demographics and medical history, including confirmation of lesion size;
- Record prior and concomitant medications, including information on any thyroid-blocking drugs;
- Deliver thyroid-blocking drugs for next visit (only patients eligible for and continuing to another cycle);

Note: Patients will not take the thyroid-blocking drugs at this visit but will be instructed to take them 24 hours prior to their next visit (ie, 24 hours prior to study drug administration).

- Perform urine hCG testing in all female patients of childbearing potential (ie, ovulating, premenopausal, and not surgically sterile);
- Collect blood to evaluate serum for ADAs and to measure exploratory biomarkers (from patients who have consented to the procedure);

Note: Clinical laboratory tests should be performed prior to any imaging.

- Assess AEs;
- Measure weight;
- Perform physical examination;
- Measure vital signs;
- Perform clinical laboratory tests;

Note: Clinical laboratory tests should be performed prior to any imaging.

- Perform triplicate 12-lead ECGs;
- Perform echocardiogram;

Note: LVEF may alternatively be measured using a multigated acquisition scan.

- Perform urinalysis for kidney biomarkers and for microscopic evaluation of sediment; and

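### The mandatory stop for recurrent toxicity counts only Cycle 1 doses, so a repeat involving a later cycle leads to 50% resumption with no required patient-level stop

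*Combined protocol and SAP*

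**What the plan says.** Section 3.1.5.2 has six toxicity blocks: thrombocytopenia, anemia and neutropenia, renal, two hepatic blocks, and other non-hematological toxicity. The synopsis repeats them. Each block has the same structure:

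- Withhold until a recovery threshold is met, then "Resume CAM-H2 at 50% in patients with complete or partial resolution" (the thrombocytopenia block differs only in wording).
- Return to full dose in the next cycle if the reduced dose is tolerated. The renal block reads: "If a reduced dose does not result in another decrease of eGFR, administer CAM-H2 at the full, planned dose for next cycle".
- Stop permanently for a long delay, as in "Permanently discontinue CAM-H2 for eGFR decreases requiring a treatment delay of 12 weeks or longer".
- Stop permanently for toxicity that is "recurrent (defined in this study as occurring after >1 dose of CAM-H2 during Cycle 1"; the non-hematological block, for example, reads "Permanently discontinue for recurrent (defined in this study as occurring after >1 dose of CAM-H2 during Cycle 1) Grade 3 or 4 toxicities".

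Sections 3.1.1.2 and 3.1.2.2 allow up to four cycles in escalation and two in expansion, with two doses per cycle. Entry to a further cycle needs clinical benefit and a cumulative kidney dose below 23 Gy. For the Week 11 review, Section 6.2.2.9 says "Cycle 2 eligibility will be assessed by evaluating disease state and safety" (Section 6.3.2.9 says the same for expansion), and Section 6.2.3.10 says "this visit will also serve as eligibility assessment for the next cycle in patients with CB and a cumulative kidney dose <23 Gy".

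**The concern.** The recurrence stop is tied to Cycle 1, but the steps around it are not: they refer to the next cycle and so govern later dosing. Two qualifying toxicities after the two Cycle 1 doses must end treatment. The same two events spread over Cycles 1 and 2, or both in escalation Cycle 2 or 3, do not have to, although the patient has by then received more cumulative radiation.

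Two sequences show the effect.

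- **Sequence A:** toxicity after Cycle 1 Dose 2, recovery, Cycle 2 Dose 1 at 50%, toxicity again. The written action is to withhold and resume at 50%. If 50% means half the planned dose, that is the dose that was just not tolerated.
- **Sequence B:** toxicity after Cycle 1 Dose 1, a clean 50% Dose 2, full-dose Cycle 2 Dose 1, toxicity again. The written action is again to withhold and resume at 50%.

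At stake is whether a patient is retreated after a second qualifying toxicity because the plan requires a decision to do so, or only because no stop is written. A Cycle 1 limit makes sense in Section 3.1.4.1, where the same parenthetical defines DLTs. The protocol gives no reason for carrying it into individual dose modification.

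**Working it through.** **1. Does another section supply the stop?**

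- Section 3.1.4.1: DLTs are confined to Cycle 1.
- Section 3.1.5.1: a related SAE in one patient, or related severe AEs in two patients of a cohort, pauses dosing in the study for review. The pause is temporary, at study level, and not tied to recurrence in a patient.
- Section 4.3: withdrawal for an AE is permitted, not required.
- Sections 6.2.2.9, 6.2.3.10 and 6.3.2.9: eligibility for the next cycle has no recurrence criterion.

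None requires a permanent stop for the patient on a repeat.

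**2. Which repeats does the rule catch?** List the pairs of doses after which a toxicity could occur, and keep those with a planned dose still to come.

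- Escalation, 8 doses: 8 × 7 / 2 = 28 pairs; 21 leave a further dose; 1 (both Cycle 1 doses) is caught. Of the 20 missed, 18 span cycles and 2 lie within Cycle 2 or Cycle 3.
- Expansion, 4 doses: 4 × 3 / 2 = 6 pairs; 3 leave a further dose; 1 is caught. The 2 missed both end at Cycle 2 Dose 1, leaving one dose, Cycle 2 Dose 2 at 50%.

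These are schedule combinations, not probabilities.

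**3. How many escalation doses remain after the repeat?** Section 1.3.2 gives 34.9 ± 2 mGy/mCi to the kidneys with amino acids. Its own figures reproduce: 400 mCi × 34.9 = 13.96 Gy (stated 14 Gy), and 23 Gy / 34.9 mGy/mCi = 659 mCi (stated 659).

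Assumptions: Sequence A with a full-dose Cycle 1; 50% means half the planned dose; the 23 Gy cap includes the cycle about to start; and Cycle 2 Dose 2 at 50% is clean, so the next cycle returns to full dose as Section 3.1.5.2 directs. Entries are cumulative Gy, except the per-dose and count columns.

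| Level | Per full dose | After Cycle 1 | After Cycle 2 at 50% | After full Cycle 3 | After full Cycle 4 | Doses left after the repeat |
|---|---|---|---|---|---|---|
| 1 | 1.745 | 3.49 | 5.235 | 8.725 | 12.215 | 5 |
| 2 | 3.49 | 6.98 | 10.47 | 17.45 | 24.43, barred | 3 |
| 3 | 5.235 | 10.47 | 15.705 | 26.175, barred | – | 1 |
| 4 | 6.98 | 13.96 | 20.94 | 34.90, barred | – | 1 |

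The counts hold across ±2 mGy/mCi. The closest case is Level 2 Cycle 4: 700 mCi × 32.9 = 23.03 Gy, still barred. Sequence B has the same cumulative activity after Cycle 2 (two full and two half doses), so it gives the same counts at Levels 2 and 3.

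If every later dose stays at 50%:

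- Level 2: 6.98 + 3 × 3.49 = 17.45 Gy, 5 doses left.
- Level 3: 10.47 + 2 × 5.235 = 20.94 Gy, 3 doses left.

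Staying at 50% generally requires yet another toxicity in a reduced-dose cycle, so these are upper counts under this cap reading. If instead the cap counts only dose already received, then even with re-escalation 5 remain at Level 2 (17.45 < 23 before Cycle 4), and 3 each at Level 3 (15.705 < 23 before Cycle 3) and Level 4 (20.94 < 23 before Cycle 3).

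**The case against.** The strongest reply is that this is a deliberate, explicit definition with real safeguards around it. Later cycles are optional and need clinical benefit. The Week 11 safety assessments must be completed and reviewed first. Dosing is withheld to a recovery threshold and then halved, a 12-week delay ends treatment, and the Medical Monitor reviews data continuously. One related SAE in any cycle pauses dosing in the study. Investigator discretion for refractory patients who are benefiting is defensible. All of this stands, and it narrows the gap mainly to non-serious, recovered repeats. It does not supply the stop that the protocol itself requires in Cycle 1.

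A reader might infer more than the documents support:

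- **That the kidney-dose totals show harm.** They do not. Level 3 with all later doses at 50% totals 20.94 Gy, exactly what two uncomplicated full cycles give (4 × 5.235), which the protocol permits. The dose at the Sequence A repeat, 10.47 + 2.6175 = 13.09 Gy, is below the 14 Gy predicted for one Level 4 cycle. Kidney dose also bears directly on only one of the six blocks.
- **That three to five further doses are typical at Levels 2 and 3.** Under the stated cap reading, the counts of 5 and 3 depend on staying at 50%; ordinary re-escalation gives 3 and 1.
- **That retreatment at the failed dose is certain.** The text does not say 50% of what. If it means half the previous dose, a repeat on a reduced dose leads to a further reduction, but still to no mandated stop.

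The parenthetical could also be read as any time after the second Cycle 1 dose. Every first toxicity in a later cycle would then be recurrent, leaving the later-cycle resumption steps without effect. Its use in the Cycle 1-only DLT list points to the narrower reading.

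**Conclusion.** The gap is real and modest, and worth closing. As written, a second qualifying toxicity that involves a later cycle and delays treatment by less than 12 weeks leads to 50% resumption with no mandated patient-level stop. Expansion, where at least 52 patients in total are to receive the chosen dose, exposes at most one further dose per affected patient. The escalation counts rest on non-human-primate predictions and the listed readings of the 50% rule and the cap. How many patients would be affected cannot be derived from the documents. The gap disappears once no dose remains: after the last dose of escalation Cycle 4 or of expansion Cycle 2. A reader might also infer that dose finding is compromised; it is not, because DLTs and the MTD rule use Cycle 1 only. Confidence in the reading of the text is high; the case for change rests on consistency with the sponsor's own Cycle 1 standard, not on demonstrated excess risk.

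**What to change.** Keep the Cycle 1 definition for DLTs in Section 3.1.4.1. In the six blocks of Section 3.1.5.2 and their synopsis copies, replace the parenthetical with: *defined as a second occurrence of toxicity meeting this block's criteria, following a different dose of CAM-H2 from the first occurrence, in the same or any later cycle*.

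The words *second occurrence* matter. Simply counting doses across all cycles could be read to catch a first-ever toxicity in a later cycle, which should still lead to withholding and 50% resumption.

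The cost is one parenthetical in six bullets plus their six synopsis copies, with no added visits, assessments or patients. The downside is earlier stopping for some patients with clinical benefit, including for two recovered Grade 2 thrombocytopenias in different cycles. In the broad non-hematological block, two different Grade 3 events would also count. If the sponsor prefers to allow retreatment after a later-cycle repeat, the protocol should say so and give the reason.

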3.1.4.1 Definition of dose-limiting toxicities

DLTs are defined as toxicities occurring **only** within Cycle 1 (ie, the approximately 12-week [84-day] period that includes 2 administrations of the study drug given 4 weeks apart [including the 4-week Safety Follow-Up Period after Dose 1]). DLTs include ≥ 1 of the following:

- Study drug-related SAE in at least 1 patient in 1 cohort;
- Severe study drug-related AE in at least 2 patients in 1 cohort;
- Any death not clearly due to the underlying disease or extraneous causes;
- Development of severe renal failure (estimated glomerular filtration rate [eGFR] <30 mL/min) or a drop of >40 mL/minute in eGFR;
- Any seizure activity that is considered to be study drug-related;
- Grade 3+ thrombocytopenia with bleeding;
- Recurrent (defined in this study as occurring after >1 dose of CAM-H2 during Cycle 1) Grade 3 or 4 thrombocytopenia;
- Grade 4+ neutropenia or thrombocytopenia >7 days;
- Recurrent (defined in this study as occurring after >1 dose of CAM-H2 during Cycle 1) Grade 3 or 4 anemia and/or neutropenia;
- Recurrent (defined in this study as occurring after >1 dose of CAM-H2 during Cycle 1) Grade 3 or 4 non-hematological toxicities as listed in the Common Terminology Criteria for Adverse Events (CTCAE) version 5.0;
- An alanine aminotransferase (ALT) or aspartate aminotransferase (AST) $>3 \times$ upper limit of normal (ULN) accompanied by a total bilirubin of $>2 \times$ ULN (Hys Law);
- Grade 3 or 4 fatigue for >1 week;
- Grade 3 or 4 electrolyte abnormalities that last >72 hours or any Grade 3 or 4 electrolyte abnormalities associated with clinical signs and symptoms of any duration;
- For patients with hepatic metastases, AST or ALT $>8 \times$ ULN or AST or ALT $>5 \times$ ULN for ≥ 14 days;
- An absorbed dose to the kidneys >23 Gy;
- An absorbed dose to the bone marrow >2 Gy; or
- Other clinically significant changes in vital signs, clinical laboratory tests, ECGs, or other safety parameters deemed as a significant safety concern by the Investigator.

All AEs of the specified grades will count as DLTs, except those that are clearly and incontrovertibly due to disease progression or extraneous causes.

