3.1.5 Stopping Rules, Dose Modifications, and Missed Doses

3.1.5.1 Stopping rules

During the dose escalation phase, the SRC will meet to decide on the continuation of dosing after the completion of 1 full treatment cycle in at least 3 patients at each dose level. During the dose expansion phase, the SRC will formally meet after the completion of 1 full treatment cycle in every 9 patients to review all emerging safety and tolerability data. All data must be available to the SRC ≤ 3 weeks after the last dose in the cohort. Additional details are described in the SRC Charter.

Safety and tolerability data; however, will be reviewed on an ongoing basis by the Medical Monitor, and stopping rules will be applicable starting with dosing of the first sentinel patient. SRC decisions will be based on the following:

- If a study drug-related SAE occurs in 1 patient or if a study drug-related severe AE occurs in 2 patients in the same cohort, the dosing in the study should be temporarily stopped in order to review additional safety data. If after review of the additional data, the study drug-relatedness assessment changes, the study can resume without substantial amendment;
- If 2 patients in a cohort experience a DLT that is related to CAM-H2 administration, dosing will be stopped until resolution of the DLT. Doses can be adapted as per the modification schemes in [Section 3.1.5.2](#);

- If at least 1 DLT is reported, the SRC recommendation will depend on the DLT profile (ie, identical DLTs in different patients), the frequency and severity of DLTs in the same patient, and the recommendation made by the Investigator; and
- If no DLT is reported, the planned dose escalation may proceed with the next cohort or phase, unless the Investigator has any other safety concerns.

All decisions will be documented in writing and communicated to the study team in a timely manner before dosing in the next cohort can start.

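### If the renal DLT is a fall from baseline, a patient starting above eGFR 100 mL/min can have that DLT without meeting the renal hold rule, and no written rule may govern the next dose

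*Combined protocol and SAP*

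**What the plan says.** The renal DLT in Section 3.1.4.1 has two limbs: eGFR below 30 mL/min, "or a drop of >40 mL/minute in eGFR". The second is absolute, and the text does not say what the drop is measured from. DLTs count only in Cycle 1.

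The renal dose-modification rule in Section 3.1.5.2 starts from a different definition: "Renal toxicity (defined as an eGFR <40 mL/minute or a 40% decrease in baseline eGFR". When it is met, dosing is withheld until eGFR is back to at least 80% of baseline, then resumed at half dose. One of its further clauses reads: "Permanently discontinue CAM-H2 for eGFR decreases requiring a treatment delay of 12 weeks or longer". The synopsis carries the same two definitions.

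For a single DLT, Section 3.1.5.1 says: "If at least 1 DLT is reported, the SRC recommendation will depend on the DLT profile". A mandatory stop needs more: "If 2 patients in a cohort experience a DLT that is related to CAM-H2 administration, dosing will be stopped until resolution of the DLT". That second rule then points to the modification schemes in 3.1.5.2. Dosing also pauses for one related SAE, or for related severe AEs in two patients of a cohort. Safety data "will be reviewed on an ongoing basis by the Medical Monitor".

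Eligibility (Section 4.1) requires eGFR above 59 mL/min and sets no upper limit.

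**The concern.** One rule uses an absolute fall and the other a percentage fall, so at a high enough baseline a declared renal DLT can lie outside the rule meant to manage renal toxicity. The practical question is Dose 2 of Cycle 1, four weeks after Dose 1. Followed literally, the plan permits a full second dose after a renal DLT, although Section 1.3.2 predicts that the kidneys are the dose-limiting organ. By contrast, Grade 2 thrombocytopenia requires a hold and a half dose.

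The mismatch looks unintended, because the other dedicated rules reach their own DLTs. Both hepatic triggers repeat the DLT criteria, including the one that begins "Hepatic toxicity (patients with hepatic metastases and AST or ALT". The thrombocytopenia rule starts at Grade 2, and the anemia and neutropenia rule at Grade 3.

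**Working it through.** The documents give no figure of their own on this point, so the check compares the two definitions directly.

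**Inputs.** Let B be baseline eGFR and F follow-up eGFR, in mL/min.
- DLT (Section 3.1.4.1): F < 30 or B − F > 40, taking the drop as from baseline.
- Renal hold (Section 3.1.5.2): F < 40 or (B − F)/B ≥ 0.40, taking the 40% decrease as at least 40%.
- Admissible baseline (Section 4.1): B > 59, no ceiling.

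**Where a DLT escapes the hold.** F < 30 already implies F < 40, so only the absolute limb can escape. That requires 40 < B − F < 0.4B, which has a solution only if 0.4B > 40, that is, B > 100. In terms of follow-up, 0.6B < F < B − 40, a window of width 0.4B − 40. Since F > 0.6B and B > 100, F is always above 60.

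| B | Window for F | Width, 0.4B − 40 | Whole values of F | Fall, % of baseline |
|---|---|---|---|---|
| 100 | none | 0 | none | – |
| 103 | 61.8 to 63 | 1.2 | 62 | 39.8 |
| 105 | 63 to 65 | 2 | 64 | 39.0 |
| 110 | 66 to 70 | 4 | 67–69 | 37.3–39.1 |
| 120 | 72 to 80 | 8 | 73–79 | 34.2–39.2 |
| 130 | 78 to 90 | 12 | 79–89 | 31.5–39.2 |

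Window ends are excluded. In whole numbers, no baseline from 60 to 102 has an affected value. Example: 120 to 79 is a fall of 41 mL/min, and 41/120 = 34.2%. That is a DLT but not a renal hold.

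**If the drop is not from baseline.** Suppose it were measured from the previous visit. A patient with baseline 90 who rises to 100 and then falls to 58 has dropped 42 mL/min, but is only (90 − 58)/90 = 35.6% below baseline. The threshold of 100 therefore depends on the baseline reading.

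**Other written rules that might apply.**
- The general rule in 3.1.5.2 covers "Grade 3 or 4 non-hematological toxicities as listed in the CTCAE version 5.0". The documents do not reproduce the CTCAE cut-offs for eGFR, so they do not settle whether it would apply.
- The stops in 3.1.5.1 need a related SAE, or a second patient in the cohort with a related DLT or related severe AE.
- The SRC's scheduled meeting in escalation follows a full cycle (about 12 weeks) in at least 3 patients. In expansion it follows a full cycle in every 9 patients. Both come after Dose 2 at Week 4.
- The two-week sentinel review (Section 3.1.4) decides whether the rest of the cohort may be dosed, not whether the sentinel receives Dose 2.
- Visit 7 requires laboratory tests before Dose 2 (Section 6.2.2.5) but gives no eGFR cut-off. Cycle 2 needs a completed safety review (Section 3.1.1.2), also without one.

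For an isolated event that is not a related SAE and not Grade 3 or 4, what remains is the judgement of the Investigator and Medical Monitor.

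**The case against.** The two definitions serve different purposes. DLTs drive escalation, while 3.1.5.2 manages the individual patient, and the protocol nowhere promises that every DLT leads to a modification. Related seizure and a marrow dose above 2 Gy have no dedicated rule either. A percentage rule is defensible for a patient whose eGFR is still above 60 and so would still meet the entry limit. Harm would need a high baseline, a fall within a narrow band, and an Investigator and Medical Monitor who both let a declared DLT pass. Withdrawal for a clinically significant AE is available (Section 4.3), and clinically significant laboratory abnormalities must be followed up (Section 8.1).

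Most of this stands, and it sets the weight of the point. It does not show that the mismatch was chosen, and each of these safeguards is discretionary on dosing.

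The objection is strongest against the obvious repair of adding the absolute drop to the renal toxicity definition. That would import the 80% recovery level: 0.8 × 120 = 96 at baseline 120, so a patient who stayed at 73–95 would be permanently discontinued at 12 weeks. A fall from 140 to 99 (41/140 = 29.3%) would be held until 112. A fall from 60 to 40 (20/60 = 33.3%) or from 80 to 49 (31/80 = 38.75%) would still trigger no renal hold. That asymmetry is hard to defend, so the automatic hold is not recommended.

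A reader might infer that renal DLTs in general go unmanaged, or that the escalation decision is compromised. The documents support neither. At baselines of 100 or below, read as from baseline, every eGFR-based DLT triggers the renal hold. Above 100, larger falls still do. The event also counts as a DLT under Section 3.1.4.2 whatever happens to that patient's next dose.

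**Conclusion.** The mismatch is real but local. Its size is a window 0.4B − 40 mL/min wide above a baseline of 100. A patient in that window has a protocol-defined renal DLT and, absent a further qualifying feature of the event or a second such patient in the cohort, no written rule for the next dose.

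The conclusion rests on three readings: the DLT drop is measured from baseline, the 40% decrease means at least 40%, and the event is not otherwise graded or classified into another rule. The plan does not give the distribution of baseline eGFR, so the frequency cannot be computed for the maximum of 18 escalation patients or for the at least 52 to be exposed at the chosen dose. It would go too far to infer that such a patient will receive a full dose unchecked: the plan permits that, but does not require it. This is a cheap improvement that the sponsor could make, at low priority.

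**What to change.** Make three small edits, in the sections named and in the matching synopsis text:

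1. In Section 3.1.4.1, state that the drop of more than 40 mL/min is measured from baseline eGFR.
2. In Section 3.1.5.2, word the percentage trigger as a decrease of at least 40% from baseline eGFR.
3. In Section 3.1.5.2, add that after a fall of more than 40 mL/min from baseline that is less than 40%, the next dose is withheld until the Medical Monitor and Investigator document a decision to resume at full dose, resume at 50%, or discontinue. State that the 80% recovery and 12-week discontinuation clauses do not apply automatically to these patients.

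Every eGFR-based renal DLT then has a written step before the next dose, and the existing DLT threshold stays as it is. No assessment is added: in Cycle 1, laboratory tests are already scheduled at Weeks 1, 2 and 3 and before Dose 2, and Appendix B lists eGFR in the chemistry panel. The cost is an occasional short delay in a patient whose eGFR is still above 60. Because 3.1.5.2 is not limited to Cycle 1, the step would also apply in later cycles and in expansion unless the sponsor restricts it.
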